All participants will be prompted to complete EMAs once per day during the 24-week study time period. If a participant contracts COVID-19, they will click the “COVID-19 Positive” button in the app. This action will cause the app to ask a different set of questions focused on enhanced monitoring COVID-19 symptoms for the next 21 days. At the end of 21 days, the app will return to daily prompts of the pre-COVID-19 EMAs. At the conclusion of the 24-week EMA period, participants will gain access to a new button in the app that will initiate the 24-week follow-up assessment (see Appendix). Participants will receive a daily alert from the app to click the “Final Survey” button in the app to complete the end of study assessment. The 24-week phone interview (or RedCap interview if a medical condition prevents them from being able to speak for long periods of time) will be scheduled at the baseline visit and the date/time of the call will appear at the top of the app home screen. A maximum of five phone call/text attempts and one mailed letter will occur over two-week period, before data from phone interview (or RedCap interview if a medical condition prevents them from being able to speak for long periods of time) will be considered unattainable. Those participants who were loaned a mobile phone to use during the study will be mailed a stamped envelope to return the phone and charger, or will be approached by study staff to reclaim the mobile device during a routine follow-up visit in the SCC chemo infusion clinic. Upon receipt of the smartphone and charging equipment, all equipment will be sterilized with alcohol-based sanitizer in accordance with current practice guidelines put forth by the Centers for Disease Control at the time it is returned by the study subject.

EMA completion rates, participant dropout, and feedback on the participant satisfaction survey will be used to evaluate feasibility of this type of mobile intervention in this population.

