Qualitative interview data. A qualitative interview will be conducted at the end of the 24-week study period via a brief phone call (or RedCap if a medical condition prevents them from being able to speak for long periods of time). This interview will assess opinions about the app, ways the app could be improved for future patient monitoring, etc. The follow-up phone call will be recorded for transcription and analyzed using NVivo. Recordings will be transcribed by internal staff, Microsoft Transcribe, or by approved contractors with whom a Business Associates Agreement has been made. When using Microsoft Transcribe, all transcriptions will be reviewed by study staff. De-identified information will be shared with collaborators and colleagues at other NCI Designated Cancer Centers (see Aim 3).

Data from the electronic health record. Relevant data from the EHR will be extracted as needed to address any discrepancies or omissions surrounding specified study outcomes that have been collected through the smartphone EMA surveys. This supplemental information will be collected and stored in REDcap.

Private identifiable data (e.g., participant names, study assessment dates, and contact information) will be required for participant contact and thus will be collected in this study. Private identifiable data will be used to contact participants and will be saved in compliance with university storage of PHI (e.g., encryption). All printed private identifiable data will be stored in a locked filing cabinet in [name] research office when not in use and will be destroyed 12 months after data collection is completed.

Smartphone programming. The mHealth Shared Resource at the OUHSC and Stephenson Cancer Center (SCC) has developed the Insight™ mHealth Platform that empowers researchers to build, test, and launch technology-based assessment and intervention tools. The mHealth resource employs a program manager, four senior programmers, and two research technicians, who develop and maintain web and mobile applications and relational databases. Applications are developed using state-of-the-art cross-platform design tools. The Resource is located within the Oklahoma Tobacco Research Center (OTRC), where [name] office is located. [name] is the Scientific Director of the mHealth Shared Resource, which will provide the programming services for the proposed project.

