When participants provide a pattern of responses that are suggestive of heightened risk for COVID-19 (See algorithm in Appendix), they will receive a suggestion to contact SCC staff, and the app will send an encrypted email containing this information to [name] and other SCC staff with a request to contact the participant to assess symptoms (see Appendix) and whether urgent medical attention is indicated. Should urgent medical attention be warranted, the patient will be instructed to the clinical unit most appropriate to the symptoms they reported through the app algorithm or discussed with the clinical nursing or physician staff. Non-emergent patients who screen positive for COVID-19 will begin an enhanced symptom and vital sign monitoring period that will continue until the participant reports that they are no longer symptomatic and/or a medical professional informs them that they no longer need to self-quarantine, which is expected to be approximately 21 days. These patients will receive a pulse oximeter (provided by the study) and the app questions will change to include daily prompts requesting that the patient input morning vital signs (temperature, heart rate, blood oxygen levels (SpO2)) and answer questions specific to the severity of symptoms and/or emergence of new symptoms of COVID-19. If a patient is hospitalized, they can continue to complete the daily assessments if they are willing and able to do so. The app will also support check-ins with SCC staff and after-hours medical staff as needed after diagnosis of COVID-19 or until the patient has been medically released from self-quarantine. Once the participants have completed the enhanced symptom and vital sign monitoring portion of the study, the pulse oximeter will be returned to the research team at the time of their next scheduled appointment. These devices will then be sterilized with both alcohol-based sanitizing products as well as ultraviolet light exposure in accordance with practices endorsed by the Centers for Disease Control.

Participants will continue to use the app to complete a final 24-week follow-up survey and will be contacted by phone (or RedCap if a medical condition prevents them from being able to speak for long periods of time) to complete a brief qualitative interview 24 weeks after study enrollment. Relevant demographic, cancer-specific and COVID-19 related data will be extracted

from electronic health records at the conclusion of the study.

E. Chart Review

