Study staff will conduct a chart review on OUHSC campus computers using OU Medicine's electronic medical record. Chart review will be conducted after completion of the EMA period. Initial evaluation, treatment plan, and follow-up notes will be searched for the following data points:

- a) Cancer Stage at Initial Presentation
- b) Type of Cancer – text field
- c) History of Previous Cancer Diagnosis
- d) Previous Cancer Treatment
- e) History of Previous Cancer Treatment with Surgery
- f) History of Previous Cancer Treatment with Chemotherapy
- g) History of Previous Cancer Treatment with Endocrine Therapy
- h) History of Previous Cancer Treatment with Radiation
- i) History of Previous Other Types of Cancer Treatment
- j) Receiving concurrent chemotherapy and radiation
- k) Body Mass Index at start of treatment
- l) Body Mass index at end of treatment
- m) Number of no-show and cancelled office visits
- n) Referral to Supportive Care
- o) Distance in miles from the participant's home to the SCC?
- p) Does the participant reside in a rural county?

All data collected during the chart review will be assigned to the corresponding participant ID number and entered into study electronic databases in accordance with the data and safety-monitoring plan outlined below. See Appendix for a full list of data that will be collected via chart review.

F. Biospecimens

No biospecimens will be collected as part of this study.

G. Banking/Repository/Database

No biospecimens will be banked for future use. All data will be stored and accessed on OUHSC devices/computers.

H. Inclusion / Exclusion Criteria

Individuals will be included in the study if they:

- 1) Demonstrate > 6th grade English literacy level (i.e., phone based EMAs require >6th grade literacy)
- 2) Present for care at the Stephenson Cancer Center at the University of Oklahoma Health Sciences Center
- 3) Are currently receiving cytotoxic chemotherapy or immunotherapy by intravenous infusion or by orally delivered medication
- 4) Are greater than or equal to 18 years of age
- 5) Are willing and able to complete surveys on their personal smartphone or a study provided smartphone
- 6) Are willing and able to provide informed consent

There are no early termination criteria; however, individuals can elect to stop participation in

mobile app monitoring at any time.

I. Gender/Minority/Pediatric Inclusion for Research

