Aim 2. We will examine participant characteristics among those who are and are not transitioned to an Aim 2 monitoring of vital signs and severity of COVID-19 symptoms. We will also examine participant characteristics and outcomes for those that require emergent intervention versus non-emergent intervention. Among those who undergo enhanced monitoring, we will use descriptive statistics to summarize the proportion of patients experiencing the following outcomes: manifestations of severe disease, treatment related toxicity, need for hospitalization, and COVID-19 related mortality. We will also compare outcomes and tolerability of enhanced self-monitoring for severe infection and compare rates of disease related morbidity and mortality to baseline rates published in the literature. We will evaluate participant satisfaction with the app and identify ways to improve this novel patient monitoring technology. We will perform logistic regression to determine the odds of experiencing primary outcomes, based upon baseline characteristics (e.g., sex, race/ethnicity, cancer stage/type). Kaplan-Meier survival curves and log-rank tests of homogeneity will be used to identify the survival functions, describing the time to resolution of symptoms based upon

demographic characteristics. Because COVID-19 is a novel virus and we do not fully understand its impact on our patient population, this study will provide useful, granular information about the daily symptoms of and recovery from COVID-19 in cancer patients.

Aim 3. No analyses proposed, as this is a collaboration aim.

N. Data and Safety Monitoring Plan

Data quality and integrity will be held to the highest standard to ensure accurate reporting and documentation of the objectives outlined in the proposal. The Institutional Review Board and the Office of Clinical Research will monitor data and safety monitoring. The institutional plan for data and safety monitoring for all trials funded by the NCI has been adopted by the University and will be utilized for conduct of our planned proposal.

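### Aim 2 admissions and deaths outside OU Medicine can go unrecorded, which would lower the rates that are compared with the literature

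*Combined protocol and SAP*

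**What the plan says.** - **Where outcomes come from.** Section D, under the heading on data from the electronic health record, makes the app surveys the primary source and the record a supplement: "Relevant data from the EHR will be extracted as needed to address any discrepancies or omissions surrounding specified study outcomes". Section D, Study application, adds an extraction at study end: "Relevant demographic, cancer-specific and COVID-19 related data will be extracted". Neither place names a health system.
- **Which record.** Section E names one: "Study staff will conduct a chart review on OUHSC campus computers using OU Medicine's electronic medical record". It lists 16 items (a to p) on cancer history, treatment, body mass index, attendance, supportive-care referral and residence. None is an admission or a death, but the section adds: "See Appendix for a full list of data that will be collected via chart review". That Appendix is not in the text available here.
- **Reporting by sick participants.** Section D, Study application: "If a patient is hospitalized, they can continue to complete the daily assessments if they are willing and able to do so".
- **Who is in the Aim 2 denominator.** Section M summarizes outcomes among those in enhanced monitoring. According to section D, the app switches when the participant presses a button after contracting COVID-19: "This action will cause the app to ask a different set of questions focused on enhanced monitoring COVID-19 symptoms for the next 21 days".
- **What is done with the rates.** Section M reports proportions with severe disease, toxicity, hospitalization and COVID-19 death, and plans to "compare rates of disease related morbidity and mortality to baseline rates published in the literature". Section D, Study Design, hypothesizes in advance that morbidity and mortality will be better than published rates. Section B gives the benchmarks: severe infection near 40% and mortality of up to 20% in cancer patients.

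**The concern.** The two sources can fail together. App reporting is least likely in the sickest patients, and the one named record may not show care given elsewhere. An admission or death at another hospital can then leave no trace in either source. The events lost this way are the severe ones, so the losses do not average out.

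The comparator is a published rate and there is no concurrent control group with the same ascertainment, so nothing in the design cancels an undercount. Fewer recorded events look like benefit from monitoring. Section A says the data will support an application for further funding, so a favourable comparison that cannot be told apart from incomplete follow-up would matter.

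The loss could also be uneven. Section E collects distance from the centre and rural residence ("Does the participant reside in a rural county"), and patients who live further away may be more likely to be admitted elsewhere. The documents give no share of such patients.

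**Working it through.** **Is there a figure to reproduce?** No. The plan states no power, alpha, derivation of the 500, expected number of COVID-19 cases, or share of care received outside OU Medicine. What follows is illustration.

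**Inputs.** From section B: r = 40% severe and r = 20% mortality, treated as the true rates with no effect of the app. Assumed: m, the share of events missed by both sources, at 10%, 20% or 30%.

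**Two possible treatments of a missed patient.** The plan does not say which applies.

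- Counted as event-free: observed rate = r(1 - m).
- Lost from numerator and denominator: observed rate = r(1 - m) / (1 - rm).

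| m | Severe, counted event-free | Severe, dropped | Mortality, counted event-free | Mortality, dropped |
|---|---|---|---|---|
| 10% | 0.40 x 0.90 = 36.0% | 0.36 / 0.96 = 37.5% | 0.20 x 0.90 = 18.0% | 0.18 / 0.98 = 18.4% |
| 20% | 0.40 x 0.80 = 32.0% | 0.32 / 0.92 = 34.8% | 0.20 x 0.80 = 16.0% | 0.16 / 0.96 = 16.7% |
| 30% | 0.40 x 0.70 = 28.0% | 0.28 / 0.88 = 31.8% | 0.20 x 0.70 = 14.0% | 0.14 / 0.94 = 14.9% |

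Both treatments lower the rate. Dropping the patients lowers it less.

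**In counts.** Take an assumed 50 patients in enhanced monitoring, with 50 x 0.40 = 20 true severe cases, 6 of them (30%) missed. The recorded rate is 14/50 = 28%, or 14/44 = 31.8% if the six are dropped. If the six are coded unknown, the bounds are 14/50 = 28% and (14 + 6)/50 = 40%, and the upper bound recovers the truth. Any further unknowns widen the interval.

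**Effect on a comparison with the literature.** Assume an exact one-sample binomial test, one-sided at 0.025 (the plan specifies no test), no true benefit, and missed events counted as non-events. The chance of a false finding of lower rates than published is:

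| Outcome, n analysed | m = 0 | m = 10% | m = 30% |
|---|---|---|---|
| Severe, 25 | 0.9% | 2.5% | 13.0% |
| Severe, 50 | 1.3% | 4.9% | 32.5% |
| Severe, 100 | 2.5% | 12.5% | 71.5% |
| Mortality, 25 | 0.4% | 0.7% | 2.3% |
| Mortality, 50 | 1.8% | 4.0% | 15.3% |
| Mortality, 100 | 1.3% | 3.9% | 24.1% |

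If the missed patients are dropped instead, the severe-disease figures at m = 30% fall to 6.3%, 15.0% and 39.3% for n = 25, 50 and 100. The distortion is modest with few cases and grows with the number of cases.

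**The case against.** A reader might infer that the plan treats an empty OU Medicine record as proof of no event. The documents do not support that. Section D says the record is used to settle discrepancies and omissions, section M says descriptive statistics, and neither says how an unobserved outcome is coded. What is missing is a rule.

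Other objections carry weight:

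- Section E's listed items are not outcomes, and its full list is in an Appendix not available here. The wording of the week-24 health questions and interview is also unseen, and a question about outside admissions may already be there. Reading section E's record as the one meant in section D is natural but not stated, and the OU Medicine record may show some outside encounters.
- Several contact routes exist: follow-up of participants who miss surveys (sections D and J), staff contact after alerts and check-ins after diagnosis, return of oximeters and loaned phones, and up to five calls or texts plus a letter at week 24 (section D). These would recover some events. They are not a vital-status procedure, though, and after the last attempt the interview is treated as unobtainable.
- The benchmarks describe cancer patients generally, with mortality stated as an upper figure. Enhanced monitoring is for patients triaged as non-emergent, so 40% and 20% may not be their true rates.
- With 50 patients, the standard error of a 40% rate is sqrt(0.40 x 0.60 / 50) = 6.9 points, so a shift of 4 points (m = 10%) lies within sampling error.

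These points limit how firmly any size can be stated. They do not supply an outcome source for care elsewhere or a rule for unknown outcomes.

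**Conclusion.** The concern holds as a gap in ascertainment and in the handling of missing outcomes. Followed as written, the visible plan can miss admissions and deaths outside OU Medicine, and such misses lower the Aim 2 rates in the hypothesized direction under either treatment of the patient.

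The size cannot be determined. The 36-28% and 18-14% figures rest on an assumed 10-30% of events missed, on the section B benchmarks being the true rates, and on missed patients being counted as non-events. They are not an estimate of what will happen. Nor do the distance and rural fields show that many patients live far away.

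The direction applies to this mechanism only. If patients who stayed well were also lost from the denominator, that would push the other way, and the plan does not address that either.

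This affects the secondary comparison in Aim 2. Aim 1, the primary aim, rests on survey completion and satisfaction and does not depend on it.

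**What to change.** In section D (data from the electronic health record) and section M (Aim 2):

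1. Name every source of outcome data, and say whether the OU Medicine record includes encounters elsewhere.
2. Code each Aim 2 outcome as event, no event or unknown. Code no hospitalization only when the participant confirms no admission at any hospital, at week 24 or at a staff contact after the illness. Code alive on any contact or OU Medicine encounter dated after the illness window, which the text should define. A later OU Medicine visit shows survival but does not exclude an earlier admission elsewhere. Everything else is unknown.
3. Report the number unknown, overall and by the distance and rural fields already collected. Give each rate with best-case bounds (unknowns as no event) and worst-case bounds (unknowns as events) before setting it beside published rates. The bounds cover only patients in the denominator, so also state how many enrolled participants have unknown status at week 24.
4. Unless the Appendix instruments already do so, ask at the planned week-24 contact about any hospital or emergency stay outside OU Medicine. Record vital status when it is learned during the planned attempts, within the consent and the confidentiality terms of sections K and P. Those terms restrict release of participant information, so speaking with third parties needs checking against them.

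The cost is a coding rule, a short addition to contacts already planned, and some staff time, with no added visits or patients. The price is wider and less favourable Aim 2 rates.

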Consent process. The patient risk in this clinical study is minimal. As part of the informed consent process, patients will be made aware of how their data will be collected. Subjects who choose not to take part in the proposed study, will not be penalized or lose benefits to which they are entitled.

Loss of confidentiality. One potential risk is loss of confidentiality. The severity of harm in the case of loss of confidentiality may range from mild to severe depending upon the individual and the specific circumstances. However, the risks of participation in the study are similar to that of participation in usual in person or phone-based treatments, as loss of confidentiality may be experienced in each case. Other possible adverse events might include compromised data security and discomfort related to being asked study questions. The research team will monitor risk and report adverse events immediately to the IRB.

Intervention. Risk to subjects from the proposed intervention research is minimal. There is no known harm from the use of standard thermometers or pulse oximetry units or daily monitoring and automated reporting of symptoms to medical professionals.

Alternative Treatments. The consent form will explain that, rather than participating in this study, individuals may choose to continue treatment in accord with their oncology treatment plan at the SCC.

General Procedures to Reduce Risk. Each participant will be assigned an identification number that will be utilized in place of names in all electronic and print data files. The sheet containing the links between participant names and identifiers will be kept in locked filing cabinet when not in use and will be destroyed 12 months after data collection has been completed. All print information, including informed consent and screening questionnaires, will be stored in a separate locked filing cabinet in [name] research offices. All electronic data (with names omitted) will be maintained on the investigators' computers and all computers, electronic files will be encrypted, and password protected. Participant information will not be released to any party outside the research team at any time.

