In-person data. Participants will complete all assessments on their personal smartphone or a study provided smartphone using the Symptom Tracker (Insight™) mHealth platform app and/or the REDcap program. Participants will be instructed that they may elect to not answer questions that make them feel uncomfortable. All questionnaire data is automatically saved and password protected. To ensure that research staff are adequately trained in data collection, confidentiality, and the protection of human subjects, all project staff will complete extensive training focused on each of the following topics: 1) project rationale and objectives; 2) the informed consent process; and 3) general data collection procedures (e.g., computer data collection, privacy). They will also complete all confidentiality, conflict of interest, and HIPAA training programs as required by the University of Oklahoma Health Sciences Center.

EMA data. Participant responses to study questions will be encrypted and stored on the study/personal smartphone. Encrypted data will be automatically uploaded to our secure server each day. When/if the app determines that risk for COVID-19 infection is high, or COVID-19 symptoms are worsening (in those who contract the virus), an encrypted email will be sent from our secure server to clinical study staff that includes the participant name, date of birth and phone number. The following features are designed to ensure the security of this data: 1) the data stored on the smartphone device are in a SQLite database in a sandbox environment, where read/write operations are only available through the programming application (i.e., no file or output is readable to end users); 2) a 10-12 character password (only known to researchers) is required to authenticate the current user before data can be manually accessed; 3) the web browser application linking the investigator's computer to the database is on HTTPS protocol (SSL certificate with encryption) which will guarantee the data transfer from web browser to the backend database is well protected; and, 4) the backend database is hosted by Microsoft Azure and the University of Oklahoma Health Sciences Center. These steps will ensure the security of EMA data. Software will be downloaded onto each study phone so that study data can be remotely wiped if phones are lost or stolen.

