Beyond the above noted issues, the following step will be taken to minimize the likelihood of an adverse reaction to the study: The consent form will clearly describe the nature of the assessments and intervention. Thus, participants who feel uncomfortable with such assessments or intervention programs are not likely to agree to participate.

Potential Benefits. Potential benefits to participants include the use of study phones during the intervention period (at the current time, this benefit is estimated to be unlimited voice and text messages and 2 GB high speed data for the duration of their involvement in the study [i.e., 24 weeks]). Participants may also directly benefit from early detection of and immediate intervention upon presentation of COVID-19 symptoms. Finally, participants may also benefit from the enhanced symptom monitoring that is proposed.

Risks in Relation to Benefits. The current study involves very minimal risk to participants, and the risks of study participation are similar to that of participation in standard care (e.g., loss of confidentiality). All participants will be already seeking standard care before they are provided with any information about the research study. In addition, the knowledge gained from this study may be utilized to improve our understanding of symptom monitoring, health risk factors, and general experiences of individuals who undergo chemotherapy treatments to treat cancer.

We do not anticipate harm to research participants, but the principal investigators will monitor unanticipated problems (including serious and non-serious adverse events) and protocol deviations. Potential unanticipated problems for this project are all non-medical in nature. Unanticipated problems will be submitted within five University business days to the IRB using the Unanticipated Problem Report Form. The following information will be included in an adverse event report: date of event, attribution to data collection, and outcome of adverse events. All adverse events will also be reported in the annual report to the IRB along with a Summary of Participant Harms.

L. Multiple Sites

This is a single-site study.

M. Statistical Methods

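### The safety section calls all potential unanticipated problems non-medical and offers attribution only to data collection, so harm after an alert or triage failure could go unrecognised or be misattributed

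*Combined protocol and SAP*

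**What the plan says.** The last paragraph under Risks in Relation to Benefits (Section K) says that no harm is expected and adds: "Potential unanticipated problems for this project are all non-medical in nature". It then fixes the content of an event report: "The following information will be included in an adverse event report: date of event, attribution to data collection, and outcome of adverse events". The examples of adverse events earlier in Section K (Loss of confidentiality) are limited to confidentiality, data security and discomfort with the questions. The Intervention paragraph puts automated symptom reporting among the items with no known harm.

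The same section also contains general duties. The principal investigators will "monitor unanticipated problems (including serious and non-serious adverse events) and protocol deviations". It adds: "All adverse events will also be reported in the annual report to the IRB along with a Summary of Participant Harms". The paragraph on loss of confidentiality says: "The research team will monitor risk and report adverse events immediately to the IRB".

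The app's function is described in several places. In the Abstract, certain responses alert clinic nurses and lead to triage to home care or emergency assessment. In Section D (Study Design), self-reported data inform the level of care. In Section D (Study application), a risk pattern produces an email asking staff to contact the participant and judge "whether urgent medical attention is indicated". In Section K (EMA data), when infection risk is judged high or symptoms worsen, "an encrypted email will be sent from our secure server to clinical study staff".

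**The concern.** An app that helps to decide who is seen urgently has a foreseeable medical failure. The alert may not fire, the email may not be read in time, or the patient may be reassured by the absence of a prompt. Any of these could delay care. The safety section does not name this kind of event, and one of its sentences says that potential problems are of another kind.

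What is at stake is recognition and attribution. Staff completing an event form after an admission would have no listed category pointing to the alert pathway and no stated reason to look for a failure there. The protocol intends these data to support an R01 application and later randomized trials. A report of few or no app-related harms would be weak evidence if the form did not ask about the harm most specific to the app.

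**Working it through.** No arithmetic applies, because the plan gives no figure on this point. The check sets the sections side by side.

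1. **Does the declaration fit the app's role?** Section K describes potential problems as non-medical. The Abstract, Section D (Study Design and Study application) and Section K (EMA data) all place the app or its email between a symptom and a decision on urgent care. The two descriptions do not fit together.

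2. **Does Section K agree with itself?** Under Potential Benefits it says that participants may gain from early detection and prompt intervention. That benefit depends on the alert pathway working, so failure of the pathway has a medical consequence on the section's own reasoning.

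3. **Is failure foreseeable?** Alerts are triggered by responses, so an unanswered survey triggers none. The feasibility target in Section A is completion of more than 50% of prompts. Section D (Smartphone training) cites 82% to 87% completion in similar studies, which leaves 100 − 87 = 13% to 100 − 82 = 18% unanswered. These are not alert-failure rates, and staff may call participants whose completion is low. They show only that silent days are expected.

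4. **Can the event form attribute such an event?** The listed contents are "date of event, attribution to data collection, and outcome of adverse events". No item refers to the alert, the triage step or staff response.

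5. **Do other planned data close the gap?** Not on the text available.
   - Section M (Aim 2) summarises severe disease, toxicity, hospitalization and mortality among participants on enhanced monitoring. Section D (Study application) starts that monitoring for non-emergent patients who screen positive, so a missed alert can come before it.
   - Section M also compares participants needing emergent and non-emergent intervention, but does not ask whether an alert preceded the event.
   - The sixteen items listed in Section E (Chart Review) include no hospitalization, death or alert response, and the review takes place after the EMA period.
   - Section D provides for COVID-19 related data to be taken from the health record at study end, and for other record data as needed. Neither is described as a safety check on alerts.

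6. **Do the general reporting routes stay open?** Yes. The duties in Section K, the institutional monitoring plan adopted in Section N and the investigators' continuous monitoring in Section N are not limited to non-medical events. None of them, as written, names an alert or triage failure.

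**The case against.** The strongest counter-argument is that the general duties already cover a medical event. Adverse events, serious or not, and protocol deviations are monitored and reported, and the institutional plan applies as well. **This stands.** A reader might infer that a harmful missed alert would escape capture altogether, or that the non-medical sentence operates as an exclusion rule. The documents do not support either reading. The sentence is worded as an expectation, and the reporting duties around it carry no medical exclusion.

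It can also be said that the app is the data-collection system, so an alert failure could be entered under attribution to data collection, and that the listed contents are not stated to be exhaustive. **This stands in part.** A careful investigator could use the field that way. The label does not invite it, though, and would not separate an alert failure from, for example, a privacy breach or distress at a question.

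Third, care does not hang on the email alone. A risk pattern also prompts the participant to contact the clinic, the app has a button for calling clinic staff, participants can report new symptoms themselves, and standard cancer treatment continues. **This stands** and lowers the likely frequency of harm. It does not cover a survey left unanswered or an algorithm that fails to flag.

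Finally, the algorithm and the full chart-review list are in an Appendix, and the institutional plan is only referred to. Alert failures may be defined or logged there. **This stands as a limit on the conclusion.**

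**Conclusion.** The point holds in a limited form. The non-medical sentence and the single attribution item conflict with the app's triage role and with the medical benefit that Section K claims. A hospitalization or death after a failed, delayed or false-negative alert could be reported through the general routes, but it could go unrecognised as an alert or triage failure, or be attributed to something else, because no such category is stated.

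The size cannot be given as a number. The documents state neither an expected count of COVID-19 cases nor a rate of alert failure, so any count of affected participants would be assumed. A reader might also infer that the minimal-risk statement is a circular study finding. In the protocol it is a prospective statement about risk, not a planned result.

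The conclusion assumes that the Appendix and the institutional monitoring plan do not already supply the missing category. If they do, what remains is to correct the sentence and cross-refer. In either case the change is worth making, since the conflict is in the protocol text and is cheap to remove.

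**What to change.** 1. In Section K, delete the sentence on non-medical problems, or qualify it so that it does not extend to the alert and triage function.
2. Name, among potential unanticipated problems, any failed, delayed or false-negative alert followed by an emergency visit, hospitalization or death.
3. Add *app, alert or triage pathway* as an attribution category in the adverse event report.
4. When such an event is reported, check the attribution against the app's records, which Section D (EMA types) already says are date- and time-stamped.
5. If the Appendix or the institutional plan already defines or logs these events, cite it in Section K.

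The cost is protocol wording, one field on the event form, some work linking app records to reported events, and a few more reports to the IRB. Admissions for other reasons will be common in patients on chemotherapy or immunotherapy, so some judgement on attribution will be needed. Limiting the check to events that are reported keeps that work bounded. How these events are managed clinically is for the investigators, and the change does not touch it.
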